8.6.3. Laboratory Evaluations

Selected laboratory data will be summarized using only observed data. Data and change from baseline at all scheduled time points will be summarized.

Graded laboratory abnormalities will be defined using the grading scheme in DAIDS Table for Grading the Severity of Adult and Pediatric Adverse Events, Version 2.1 dated July 2017.

Incidence of treatment-emergent laboratory abnormalities, defined as values that increase at least 1 toxicity grade from baseline at any time post baseline up to the end date of the study, will be summarized by treatment group. If baseline data are missing, then any graded abnormality (ie, at least a Grade 1) will be considered treatment-emergent.

Laboratory abnormalities that occur before the first dose of study drug or after the subject has been discontinued from treatment for more than 30 days will be included in a data listing.

CCI

[REDACTED]

[REDACTED]

8.8. Adjustments for Multiplicity

The statistical analysis plan will include alpha spending considerations for the primary endpoint. No other adjustments for multiple comparisons are planned.

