8.2. Planned Analyses

8.2.1. Interim Analysis

Prior to the final analysis, the primary analysis of the primary endpoint will be conducted, additional interim analyses may be conducted, and the analyses may be submitted to regulatory agencies to seek guidance for the overall clinical development program or for other purposes.

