8.2.1.1. DMC Analysis

The DMC will review safety data on a regular basis. The DMC will review safety and efficacy data at the time of the primary analysis.

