8.5. Efficacy Analysis

8.5.1. Primary Analysis

The primary endpoint will be analyzed using a proportional odds model including baseline clinical status as a covariate. Each RDV group will be compared to the SOC group. The null hypothesis being tested is whether the odds of improvement on the ordinal scale is the same for the SOC group and either RDV group (ie, whether the common odds ratio is equal to 1). The odds ratio and 95% confidence interval for each comparison will be provided.

The proportion of subjects in each category will be summarized by treatment group. The validity of the proportionality assumption will be evaluated.

If a participant is discharged prior to Day 11, the Day 11 ordinal scale category is considered to be not hospitalized. If a participant dies prior to Day 11, the Day 11 ordinal scale category is considered to be death. Every effort will be made to obtain clinical status data for all subjects prior to discharge.

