8.9. Sample Size

The sample size computation is based on an assumed distribution of the 7-point ordinal scale on Day 11 for the SOC treatment group. The odds ratio represents the odds of improvement in the 7-point ordinal scale for an RDV treatment group relative to the SOC treatment group. The sample size needed to detect a given odds ratio for a 1:1 randomization using a 2-tailed test at level α is given by:

$$12 (z_{\alpha/2} + z_{\beta})^2 / \theta^2 (1 - \sum_{i=1}^7 \rho_i^3)$$

Where θ is the log odds ratio, ρ_i is the overall probability (combined over both treatment groups) of being in the i th category of the ordinal outcome, and $z_{\alpha/2}$ and z_{β} are the $1 - \alpha/2$ and β quantiles of the standard normal distribution {Whitehead 1993}.

A sample size of 600 participants (200 in each group) achieves > 85% power to detect an odds ratio of 1.8 using a two-sided significance level of 0.05 for comparing each RDV group (n = 200) to standard of care group (n = 200). In this sample size calculation, it is assumed that the probability distribution of the ordinal scale at Day 11 for Treatment Group 3 is as follows:

1. Death, 0.5%
2. Hospitalized, on invasive mechanical ventilation or ECMO, 2.5%
3. Hospitalized, on non-invasive ventilation or high flow oxygen devices, 7%
4. Hospitalized, requiring low flow supplemental oxygen, 8%
5. Hospitalized, not requiring supplemental oxygen - requiring ongoing medical care (COVID-19 related or otherwise), 15%
6. Hospitalized, not requiring supplemental oxygen - no longer requires ongoing medical care (other than per protocol RDV administration), 27%
7. Not hospitalized, 40%

The sample size calculation was done using software PASS (Version 14.0).

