8.10. Data Monitoring Committee

An external Independent Data Monitoring Committee (IDMC) includes independent experts that do not have direct involvement in the conduct of the study. The IDMC will review the progress of the study and perform interim reviews of efficacy and safety data, and provide recommendation to Gilead whether the nature, frequency, and severity of adverse effects associated with study treatment warrant the early termination of the study in the best interests of the participants, whether the study should continue as planned, or the study should continue with modifications. The IDMC's specific activities will be defined by a mutually agreed charter, which will define the IDMC's membership, conduct and meeting schedule.

While the IDMC will be asked to advise Gilead regarding future conduct of the study, including possible early study termination, Gilead retains final decision-making authority on all aspects of the study.

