2. TYPE OF PLANNED ANALYSIS

2.1. Interim Analyses

2.1.1. Data Monitoring Committee Analysis

The data monitoring committee reviewed the results from the primary analysis.

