2.1.2. Primary Analysis

The primary analysis was performed after data were available from participants in Part A of the study who completed 11 days or prematurely terminated from Part A of the study on or prior to Day 11. This analysis was described in the Part A Primary Analysis SAP dated 25 May 2020. This is considered as the primary analysis of the study, but most of the analyses were repeated in the Part A Final Analysis.

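### Does the open wording on alpha spending in Protocol 8.8 undermine the >85% power stated in Protocol 8.9?

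*Protocol*

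**What the plan says.** Protocol 8.5.1 sets two primary comparisons with a common control: "Each RDV group will be compared to the SOC group". It gives no testing order, alpha split or rule for declaring success.

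Protocol 8.8 is the protocol's only text on multiplicity: "The statistical analysis plan will include alpha spending considerations for the primary endpoint. No other adjustments for multiple comparisons are planned".

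Protocol 8.9 says that 600 participants, 200 per group, "achieves > 85% power to detect an odds ratio of 1.8 using a two-sided significance level of 0.05 for comparing each RDV group" with SOC. SAP 1.3 repeats this.

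On looks at the data, Protocol 8.2.1.1 says "The DMC will review safety and efficacy data at the time of the primary analysis". Two other places are looser: Protocol 8.2.1 says "additional interim analyses may be conducted", and Protocol 8.10 has the committee "perform interim reviews of efficacy and safety data". SAP 2.1.1 reports in the past tense that "The data monitoring committee reviewed the results from the primary analysis", and SAP 2.1 lists no earlier efficacy look.

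The supplied SAP covers Part B. It does no formal testing (SAP 3.3 and 3.5) and leaves the primary endpoint out (SAP 6.1). For the primary analysis it points elsewhere: "This analysis was described in the Part A Primary Analysis SAP dated 25 May 2020".

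**The concern.** Alpha spending usually refers to repeated looks over time. Under a heading about multiplicity, next to a sentence ruling out other adjustments for multiple comparisons, it could equally mean dividing alpha between the 5-day and 10-day regimens. Protocol 8.8 does not say which.

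Two things could be at stake. If the two comparisons were both tested at 0.05 with nothing to control the pair, the chance of at least one false positive would exceed 5%. If instead alpha were divided between them, the power in 8.9, computed at an undivided 0.05, would overstate the power of the deciding test, perhaps to below the stated 85%.

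**Working it through.** **Inputs (Protocol 8.9).** SOC Day 11 distribution, categories 1 to 7: 0.5, 2.5, 7, 8, 15, 27, 40% (sum 100%). Odds ratio 1.8; 200 per group, so N = 400 per comparison; two-sided alpha 0.05.

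**1. Reproduce the stated power.**
- Dividing the cumulative SOC odds by 1.8 gives the RDV distribution: 0.28, 1.41, 4.12, 5.06, 10.61, 23.97, 54.55%.
- Mean category probabilities p over the two groups: 0.39, 1.96, 5.56, 6.53, 12.81, 25.49, 47.27%. The sum of p³ is 0.1248, so 1 − Σp³ = 0.8752.
- The protocol's formula solved for power is Φ(θ·√[N(1 − Σp³)/12] − z), with θ = ln 1.8 = 0.5878.
- θ·√(400 × 0.8752/12) = 0.5878 × 5.401 = 3.175.
- Power = Φ(3.175 − 1.960) = Φ(1.215) = **88.8%**. A rank-sum simulation with 10,000 runs gave 88.6%.
- Total size for 85% power: 12 × (1.960 + 1.036)² / (0.5878² × 0.8752) ≈ 357. The planned 400 exceeds it, so >85% is right.

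**2. If alpha spending covers the two comparisons.** The procedure is not in the supplied documents, so these are illustrations. The two test statistics share the SOC arm and have correlation 0.5 with equal groups.

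| Procedure, familywise 5% | Power for one regimen at OR 1.8 |
|---|---|
| Fixed sequence, first test | Φ(3.175 − 1.960) = 88.8% |
| Hochberg, both regimens at OR 1.8 | 87.4% |
| Holm, both regimens at OR 1.8 | 86.7% |
| Dunnett (critical value 2.212, alpha 0.0270) | Φ(3.175 − 2.212) = 83.2% |
| Hochberg, other regimen at OR 1.0 | 82.8% |
| Holm, other regimen at OR 1.0 | 82.6% |
| Bonferroni (alpha 0.025) | Φ(3.175 − 2.241) = 82.5% |

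In a fixed sequence the second test succeeds only if both do: 81.4% if both regimens have OR 1.8. The odds ratio detectable with 85% power is 1.74 at 0.05, 1.83 with Dunnett and 1.84 with Bonferroni.

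**3. If alpha spending covers one interim look only.** Timing is not given, so 1/3, 1/2 and 2/3 of the information are assumed. For one comparison at 0.05, O'Brien-Fleming-type spending gives 88.4 to 88.8% and Pocock-type 85.2 to 85.9%. The >85% holds throughout. This reading alone leaves the two comparisons unadjusted.

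**4. If nothing controls the pair.** With both comparisons at 0.05 the familywise error is 9.1% (upper bound 0.05 + 0.05 = 10%). The documents do not establish that this was done.

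**5. Which reading the text favours.** The heading of 8.8, its exclusion of other adjustments for multiple comparisons, the committee's efficacy review at the time of the primary analysis (8.2.1.1), and the absence of an earlier efficacy look in SAP 2.1 all point to the two comparisons. Only the permissive wording in 8.2.1 and 8.10 points to interim looks.

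**The case for a change.** The case for acting is that 8.8 really is ambiguous and that the answer decides whether >85% describes the deciding test. It holds under one interim look, and for the first test of a fixed sequence. It fails under Bonferroni or Dunnett, and under Holm or Hochberg if only one regimen works. The 9.1% familywise error without control is not trivial. One sentence in 8.8 would remove the doubt.

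The ambiguity and the arithmetic stand. The step to a defect does not. Protocol 8.8 expressly leaves the procedure to a SAP, and SAP 2.1.2 identifies the document that describes the primary analysis. Leaving such detail to a SAP is normal practice, and that SAP may state both the procedure and its level. The 9.1% assumes that no procedure exists.

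Nor can the power statement be faulted as unlabelled. Protocol 8.9 and SAP 1.3 give the alpha, the sidedness, the group sizes and the fact that it applies to each RDV group against SOC. Only the word unadjusted is absent, and a reader can supply it.

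Timing also counts against action. SAP 2.1.1 to 2.1.3 report the primary and Part A final analyses as already done. A companion power figure in 8.9 would now alter no test or result, and it could not be calculated without the Part A SAP.

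**Conclusion.** No change to the plan. Protocol 8.8 leaves the scope of alpha spending open, but this is missing detail deferred to a named and dated SAP. It is not evidence of lost error control or of a wrong power figure. The >85% is correct at 88.8% on the basis printed beside it.

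Among the procedures tabulated, any shortfall in the power for one regimen is small: 85 − 83.2 = 1.8 points for Dunnett, 85 − 82.5 = 2.5 for Bonferroni, and 2.2 to 2.4 for Hochberg or Holm if the other regimen has no effect. These figures rest on the SOC distribution and odds ratio in 8.9, equal groups of 200, the protocol's formula without covariate adjustment, and no dropout (none is stated).

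For a check of the 8.5.1 model adjusted for baseline status, the baseline mix had to be assumed: 5 to 30% at score 4 and the rest at score 5, with a prognostic odds ratio of 1 to 8. It gave 86.3 to 88.1% at 0.05 and 79.2 to 81.5% at 0.025. The figure at 0.05 stays above 85%, and the even-split figure falls somewhat further below it.

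Anyone who needs to know how the two comparisons were controlled should read the Part A Primary Analysis SAP. A cross-reference to it in 8.8 would help readers but would change no analysis or conclusion.

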8.9. Sample Size

The sample size computation is based on an assumed distribution of the 7-point ordinal scale on Day 11 for the SOC treatment group. The odds ratio represents the odds of improvement in the 7-point ordinal scale for an RDV treatment group relative to the SOC treatment group. The sample size needed to detect a given odds ratio for a 1:1 randomization using a 2-tailed test at level α is given by:

$$12 (z_{\alpha/2} + z_{\beta})^2 / \theta^2 (1 - \sum_{i=1}^7 \rho_i^3)$$

Where θ is the log odds ratio, ρ_i is the overall probability (combined over both treatment groups) of being in the i th category of the ordinal outcome, and $z_{\alpha/2}$ and z_{β} are the $1 - \alpha/2$ and β quantiles of the standard normal distribution {Whitehead 1993}.

A sample size of 600 participants (200 in each group) achieves > 85% power to detect an odds ratio of 1.8 using a two-sided significance level of 0.05 for comparing each RDV group (n = 200) to standard of care group (n = 200). In this sample size calculation, it is assumed that the probability distribution of the ordinal scale at Day 11 for Treatment Group 3 is as follows:

1. Death, 0.5%
2. Hospitalized, on invasive mechanical ventilation or ECMO, 2.5%
3. Hospitalized, on non-invasive ventilation or high flow oxygen devices, 7%
4. Hospitalized, requiring low flow supplemental oxygen, 8%
5. Hospitalized, not requiring supplemental oxygen - requiring ongoing medical care (COVID-19 related or otherwise), 15%
6. Hospitalized, not requiring supplemental oxygen - no longer requires ongoing medical care (other than per protocol RDV administration), 27%
7. Not hospitalized, 40%

The sample size calculation was done using software PASS (Version 14.0).

8.10. Data Monitoring Committee

An external Independent Data Monitoring Committee (IDMC) includes independent experts that do not have direct involvement in the conduct of the study. The IDMC will review the progress of the study and perform interim reviews of efficacy and safety data, and provide recommendation to Gilead whether the nature, frequency, and severity of adverse effects associated with study treatment warrant the early termination of the study in the best interests of the participants, whether the study should continue as planned, or the study should continue with modifications. The IDMC's specific activities will be defined by a mutually agreed charter, which will define the IDMC's membership, conduct and meeting schedule.

While the IDMC will be asked to advise Gilead regarding future conduct of the study, including possible early study termination, Gilead retains final decision-making authority on all aspects of the study.

9. RESPONSIBILITIES

9.1. Investigator Responsibilities

9.1.1. Good Clinical Practice

The investigator will ensure that this study is conducted in accordance with ICH E6(R2) addendum to its guideline for GCP and applicable laws and regulations including the principles of the Declaration of Helsinki.

9.1.2. Financial Disclosure

The investigator and subinvestigators will provide prompt and accurate documentation of their financial interest or arrangements with Gilead, or proprietary interests in the investigational drug during the course of a clinical study. This documentation must be provided prior to the investigator's (and any subinvestigator's) participation in the study. The investigator and subinvestigator agree to notify Gilead of any change in reportable interests during the study and for 1 year following completion of the study. Study completion is defined as the date when the last subject completes the protocol-defined activities.

9.1.3. Institutional Review Board/Independent Ethics Committee Review and Approval

The investigator (or Gilead as appropriate according to local regulations) will submit this protocol, informed consent form, and any accompanying material to be provided to the subject (such as advertisements, subject information sheets, or descriptions of the study used to obtain informed consent) to an IRB/IEC. The investigator will not begin any study subject activities until approval from the IRB/IEC has been documented and provided as a letter to the investigator.

Before implementation, the investigator will submit to and receive documented approval from the IRB/IEC any modifications made to the protocol or any accompanying material to be provided to the subject after initial IRB/IEC approval, with the exception of those necessary to reduce immediate risk to study subjects.

9.1.4. Informed Consent (or Assent)

The investigator is responsible for obtaining written informed consent or assent (age ≥ 12 to < 18 , where locally and nationally approved) from each individual participating in this study after adequate explanation of the aims, methods, objectives, and potential hazards of the study before undertaking any study-related procedures. The investigator must use the most current IRB- or IEC-approved consent form for documenting written informed consent. Each informed consent (or assent as applicable) will be appropriately signed and dated by the subject or the subject's legally authorized representative and the person conducting the consent discussion, and also by an impartial witness if required by IRB or IEC or local requirements.

9.1.5. Confidentiality

The investigator must assure that subjects' anonymity will be strictly maintained and that their identities are protected from unauthorized parties. Only an identification code and any other unique identifier(s) as allowed by local law (such as year of birth) will be recorded on any form or biological sample submitted to Gilead, IRB or IEC. No biological samples will be provided to Gilead or any central laboratory during this study. NOTE: The investigator must keep a screening log with details for all subjects screened and enrolled in the study, in accordance with the site procedures and regulations. Subject data will be processed in accordance with all applicable regulations.

The investigator agrees that all information received from Gilead, including but not limited to the investigator's brochure, this protocol, CRF/eCRF, the study drug, and any other study information, remain the sole and exclusive property of Gilead during the conduct of the study and thereafter. This information is not to be disclosed to any third party (except employees or agents directly involved in the conduct of the study or as required by law) without prior written consent from Gilead. The investigator further agrees to take all reasonable precautions to prevent the disclosure by any employee or agent of the study site to any third party or otherwise into the public domain.

9.1.6. Study Files and Retention of Records

The investigator must maintain adequate and accurate records to enable the conduct of the study to be fully documented and the study data to be subsequently verified. These documents should be classified into at least the following 2 categories: (1) investigator's study file, and (2) subject clinical source documents.

The investigator's study file will contain the protocol/amendments, paper or electronic completed subject CRFs, IRB or IEC and governmental approval with correspondence, informed consent, drug records, staff curriculum vitae and authorization forms, and other appropriate documents and correspondence.

The required source data should include sequential notes containing at least the following information for each subject:

- Subject identification;
- Documentation that subject meets eligibility criteria, ie, medical history, physical examination, and confirmation of diagnosis (to support inclusion and exclusion criteria);
- Documentation of the reason(s) a consented subject is not enrolled;
- Participation in study (including study number);
- Study discussed and date of informed consent;

- Dates of all visits;
- Documentation that protocol-specific procedures were performed;
- Results of efficacy parameters, as required by the protocol;
- Start and end date (including dose regimen) of study drug, including dates of dispensing and return;
- Record of all AEs and other safety parameters (start and end date, and including causality and severity), and documentation that adequate medical care has been provided for any AE;
- Concomitant medication (including start and end date, dose if relevant; dose changes);
- Date of study completion and reason for early discontinuation, if it occurs.

All clinical study documents must be retained by the investigator until at least 2 years or according to local laws, whichever is longer, after the last approval of a marketing application in an ICH region (ie, US, Europe, or Japan) and until there are no pending or planned marketing applications in an ICH region; or, if no application is filed or if the application is not approved for such indication, until 2 years after the investigation is discontinued and regulatory authorities have been notified. Investigators may be required to retain documents longer if specified by regulatory requirements, by local regulations, or by an agreement with Gilead. The investigator must notify Gilead before destroying any clinical study records.

Should the investigator wish to assign the study records to another party or move them to another location, Gilead must be notified in advance.

If the investigator cannot provide for this archiving requirement at the study site for any or all of the documents, special arrangements must be made between the investigator and Gilead to store these records securely away from the site so that they can be returned sealed to the investigator in case of an inspection. When source documents are required for the continued care of the subject, appropriate copies should be made for storage away from the site.

9.1.7. Case Report Forms

For each subject consented, an eCRF casebook will be completed by an authorized study staff member whose training for this function is completed in the electronic data capture (EDC) system. The eCRF casebook will only capture the data required per the protocol schedule of events and procedures. The Inclusion/Exclusion Criteria and Enrollment eCRFs should be completed only after all data related to eligibility have been received. Data entry should be performed in accordance with the eCRF Completion Guidelines (eCCGs) provided by the Sponsor. Subsequent to data entry, a study monitor will perform source data verification (SDV) within the EDC system. System-generated or manual queries will be issued in the EDC system as data discrepancies are identified by the monitor or Gilead staff, who routinely review the data for completeness, correctness, and consistency. The site investigator or site coordinator or other

designee is responsible for responding to the queries in a timely manner, within the system, either by confirming the data as correct or updating the original entry, and providing the reason for the update (e.g. data entry error). Original entries as well as any changes to data fields will be stored in the audit trail of the system. At a minimum, prior to any interim time points or database lock (as instructed by Gilead), the investigator will use his/her log in credentials to confirm that the forms have been reviewed, and that the entries accurately reflect the information in the source documents. At the conclusion of the study, Gilead will provide the site investigator with a read-only archive copy of the data entered by that site. This archive must be stored in accordance with the records retention requirements outlined in Section 9.1.6.

